#### **5.5.3 Permitted Concomitant Therapy and Rescue Therapy**

Starting from the screening visit, subjects will be instructed to use a daily non-medicated moisturizer through the end of study participation. Appropriate interventions (e.g., prescribed medications) may be performed as the investigator deems necessary to treat concomitant illnesses and/or safeguard the subjects' wellbeing. No investigational product or device may be used during the study

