## PROTOCOL SYNOPSIS

Study Title	A 24 Week, Open-Label Study to Evaluate the Efficacy and Safety of Upadacitinib in Patients with Moderate-to-Severe Prurigo Nodularis
Sponsors	[name]
Study Objectives	
Primary Objective: To explore the effectiveness of upadacitinib in patients with prurigo nodularis.
 
Secondary Objectives: To explore the safety of upadacitinib in patients with prurigo nodularis.

Study Design	A single center, open-label study of 25 subjects to assess 24 weeks upadacitinib in patients with moderate-to-severe prurigo nodularis.
Study Centers	Eczema Treatment Center of New Jersey [name]
Study Population	25 adult male and female subjects with moderate-to-severe prurigo nodularis
Main Inclusion Criteria	
 
1. Male or female adult 18-64 years of age at time of screening.
 
2. Diagnosis of prurigo nodularis for <math>\geq</math> 3 months.
 
3. Moderate-to-Severe prurigo nodularis as determined by at least 10 PN lesions on legs and/or arms and/or trunk at screening and baseline .
 
4. Failure of at least a 2-week course of medium to super potent TCS or TCS is not medically advisable for subject.
 
5. Females of childbearing potential must not have a positive serum pregnancy test at the Screening Visit and must have a negative urine pregnancy test at the Baseline Visit prior to study drug dosing. Note: subjects with borderline pregnancy test at Screening must have a serum pregnancy test <math>\geq</math> 3 days later to determine eligibility. If female, subject must be postmenopausal OR permanently surgically sterile OR for females of childbearing potential practicing at least one protocol specified method of birth control, that is effective from the Baseline Visit through at least 30 days after the last dose of study drug. Female subject must not be pregnant, breastfeeding or considering becoming pregnant during the study or for approximately 30 days after the last dose of the study drug.
 
6. Subject is a candidate for systemic therapy per investigator discretion.
 
7. Able and willing to give written informed consent prior to performance of any study-related procedures.
 
8. Subject must be in general good health as judged by the Investigator, based on medical history, physical examination.
 

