Study Endpoints	Primary Endpoint: Proportion of participants with improvement (reduction) in worst-itch numeric rating scale (WI-NRS) by $\geq 4$ from baseline to Week 12. [Time Frame: Baseline to Week 12 ]WI-NRS is a patient-reported outcome (PRO) comprised of a single item rated on a scale from 0 ("No itch") to 10 ("Worst imaginable itch). Secondary Endpoints: Proportion of patients with improvement in worst-itch numeric rating scale (WI-NRS) by $\geq 4$ from baseline to Week 24 IGA PN-S 0 or 1 at weeks 12 & 24 IGA PN-A 0 or 1 at week 12 & 24 Percent improvement of PN-S & PN-A at week 12 & 24 DLQI improvement at weeks 12 & 24 Adverse Events
References	Tessa B. Mullins, Poonam Sharma, Christopher A. Riley, Sidharth Sonthalia. Prurigo Nodularis. StatPearls [Internet]. Treasure Island (FL): StatPearls Publishing; 2021 Jan. 2020 Sep 15.  Eric H Kowalski, Diana Kneiber, Manuel Valdebran, Umangi Patel, Kyle T Amber. Treatment-resistant prurigo nodularis: challenges and solutions. Clin Cosmet Investig Dermatol. 2019 Feb 28;12:163-172. doi: 10.2147/CCID.S188070. eCollection 2019.

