#### **5.5.1.3 Upadacitinib Dosage Adjustments**

Upadacitinib will be dispensed and administered as 15mg QD at baseline. For subjects who do not achieve  $\leq$  2-point reduction in itch at week 8, upadacitinib dosage will be increased to 30mg QD. The investigator may reduce the dose to 15mg QD after week 16 per investigator discretion. If an SAE or an adverse event that is thought to be related to study drug and is not alleviated by symptomatic intervention, study drug will be discontinued. Subjects who permanently discontinue study drug under this protocol should receive standard care of prurigo nodularis treatment as prescribed by their physician.

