### **5.6.8 Early Discontinuation Procedures**

Subjects will be prematurely discontinued from the study under the following conditions:

1. Subject requests to withdraw from the study.
2. Subject experiences an adverse event that makes it difficult or intolerable for the subject to continue treatment, or increases risk to the subject, or interferes with the investigator's ability to clinically evaluate the progress of the subject's treatment.
3. Subject begins an unapproved concomitant therapy for prurigo nodularis, atopic dermatitis or another medical condition that may increase risk to the subject if continuing study treatment.
4. Subject cannot be reached / lost to follow-up.
5. The study investigator suspends or terminates the study.
6. Other unanticipated reason.

Any subject who prematurely discontinues the study should complete the week 24 (End of Study) assessments.

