### **8.2.1 Additional Statistical Considerations**

The objective of the statistical analyses is to assess the efficacy and safety of upadacitinib for the treatment of subjects with moderate to severe PN who are candidates for systemic therapy. The Primary Analysis for all efficacy endpoints will be conducted after all continuing subjects have completed the study activities up to Week 16. The Intent-to-Treat (ITT) Population consists of all randomized subjects and will be used for the efficacy analyses. A Per-Protocol Population may be defined if deemed necessary to exclude subjects with major protocol violations. The criteria to define the Per-protocol Population will be detailed in the SAP. Subjects to be excluded from the Per-Protocol Population will be finalized before week 16. The Per-Protocol Population, if defined, will be used to analyze the primary efficacy endpoint.

The Safety Population consists of all randomized subjects who received at least 1 dose of study drug. An All Upadacitinib Treated Population consists of all subjects who received at least one dose of upadacitinib in the study. This population will be used to provide a comprehensive summary of safety.

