#### **Statistical Analyses for Efficacy**

All efficacy endpoints will be analyzed on the ITT population. In addition, the primary efficacy endpoints will be analyzed in the Per-Protocol Population, if defined.

No missing data imputation will be applied, and all assessments prior to premature discontinuation from study drug will be used.

Statistical Analyses for Safety – how will data be summarized? % of patients with AEs? The safety analyses will be carried out using the Safety Population. % of patients with AE's will be assessed inclusive of physical examination, laboratory assessments, and vital sign abnormalities.

Note that missing safety data will not be imputed.

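### Section 8.2.1 gives no responder status to a subject withdrawn for starting another PN or itch therapy and, in a residual case, scores a subject who stays on study drug on assisted itch

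*Combined protocol and SAP*

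**What the plan says.** The Synopsis describes the design as "A single center, open-label study of 25 subjects to assess 24 weeks upadacitinib in patients with moderate-to-severe prurigo nodularis". The primary endpoint is the "Proportion of participants with improvement (reduction) in worst-itch numeric rating scale (WI-NRS) by" at least 4 points from baseline to Week 12. IGA PN-S and IGA PN-A responder endpoints follow at Weeks 12 and 24, with the itch responder endpoint repeated at Week 24.

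Four parts of the protocol bear on a subject who starts another therapy:

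- **Section 5.5.3** has rescue therapy in its heading but does not define rescue and names no PN or itch drug as allowed or barred. It says: "Appropriate interventions (e.g., prescribed medications) may be performed as the investigator deems necessary to treat concomitant illnesses and/or safeguard the subjects' wellbeing". The only explicit bar is on investigational products and devices.
- **Section 5.6.8, item 3** lists as a reason for withdrawal: "Subject begins an unapproved concomitant therapy for prurigo nodularis, atopic dermatitis or another medical condition that may increase risk to the subject". Which therapies are unapproved is not stated. The section adds: "Any subject who prematurely discontinues the study should complete the week 24 (End of Study) assessments".
- **Section 5.5.1.3** places ordinary PN care after study drug has ended: "Subjects who permanently discontinue study drug under this protocol should receive standard care of prurigo nodularis treatment as prescribed by their physician".
- **Section 8.2.1** gives the efficacy set: "The Intent-to-Treat (ITT) Population consists of all randomized subjects and will be used for the efficacy analyses". Its only rule on efficacy data is: "No missing data imputation will be applied, and all assessments prior to premature discontinuation from study drug will be used".

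**The concern.** The entry criteria in section 5.2.2 clear other treatments before baseline: topical therapy for 1 week, UVB for 2 weeks, oral systemic PN therapy or phototherapy for 4 weeks, dupilumab for 12 weeks. The protocol thus treats such therapies as something that would distort the itch score at entry. It has no matching rule for the score at the endpoint visit.

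Two situations arise.

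(a) The subject starts a new PN or itch therapy and is withdrawn under section 5.6.8. There is no on-drug score after that, nothing is imputed, and the plan does not say whether the subject counts as a non-responder or drops out of the calculation. The efficacy set does not settle it, because it is defined by a randomization that does not take place.

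(b) The subject starts something that relieves itch and stays on study drug, either because the therapy is not regarded as unapproved or because it was prescribed under the discretion in section 5.5.3. The stated rule then uses the score as observed, and any relief from the added therapy is credited to upadacitinib.

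With one arm, the responder rate is itself the result, and there is no concurrent group against which to judge either effect.

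**Working it through.** The plan gives no response rate, precision target or power basis for its 25 subjects, so there is no figure of its own to reproduce. It also gives no expected frequency of added therapy. The counts below are assumptions: m = 1 to 3 affected subjects of 25, and r = 6, 9 or 12 responders for case (a).

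**Case (a), withdrawn subjects.** If the m subjects leave the denominator, the rate is r/(25 − m) instead of r/25.

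| r | r/25 | m = 1 | m = 2 | m = 3 |
|---|---|---|---|---|
| 6 | 24.0% | 6/24 = 25.0% (+1.0) | 6/23 = 26.1% (+2.1) | 6/22 = 27.3% (+3.3) |
| 9 | 36.0% | 9/24 = 37.5% (+1.5) | 9/23 = 39.1% (+3.1) | 9/22 = 40.9% (+4.9) |
| 12 | 48.0% | 12/24 = 50.0% (+2.0) | 12/23 = 52.2% (+4.2) | 12/22 = 54.5% (+6.5) |

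If the denominator stays at 25, the change is zero in every cell. Both denominators fit the text.

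**Case (b), subjects who stay on study drug.** Let q be the share of affected subjects whom the added therapy turns from non-responder to responder. The rise is 100 × m × q / 25 = 4mq points.

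| q | m = 1 | m = 2 | m = 3 |
|---|---|---|---|
| 25% | 1 | 2 | 3 |
| 50% | 2 | 4 | 6 |
| 100% (upper bound) | 4 | 8 | 12 |

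Example at the upper bound, with exact (Clopper-Pearson) 95% intervals: an observed 12/25 = 48.0% (27.8 to 68.7) would, without the assisted responders, be 11/25 = 44.0% (24.4 to 65.1), 10/25 = 40.0% (21.1 to 61.3) or 9/25 = 36.0% (18.0 to 57.5) for one, two or three such subjects.

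**Scale.** The interval around 12/25 is 68.7 − 27.8 = 40.9 points wide, so every shift above lies well inside it. The interval describes sampling error, however, and does not allow for a scoring choice that inflates the rate.

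**The case against.** The strongest reply is that the protocol already sends most added PN therapy off study. Section 5.5.3 speaks of other illnesses and wellbeing, not PN treatment; section 5.6.8 withdraws for unapproved PN therapy; section 5.5.1.3 puts standard PN care after discontinuation; and poor itch response at Week 8 appears to be met by raising the dose to 30 mg. This stands, and it makes case (b) the residual one. It does not close it, because the key term is undefined and the reference to increased risk can be read as narrowing the trigger.

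A second reply is that case (b) is governed by a rule: on-drug scores count as observed. That is also right. The issue there is whether that rule suits a responder rate meant to describe upadacitinib, which is partly a choice of estimand.

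Third, the reference to randomization looks like template text, and the natural meaning is all enrolled subjects, which would make case (a) zero. That reading is reasonable, but a missing score still has no stated status under a no-imputation rule. The same denominator question touches every dropout; this is one instance of it.

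Fourth, a Per-Protocol set is allowed for. It is optional, its criteria are left to the SAP, it would serve only the primary endpoint, and it leaves the ITT result unchanged.

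A reader might go further in three ways that the documents do not support:

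- That Week 24 scores collected after withdrawal, possibly under standard care, enter the analysis. The ordinary reading of section 8.2.1 excludes scores taken after study drug stops.
- That any systemic corticosteroid course should make a subject a permanent failure. The itch item covers only the past 24 hours (section 5.6.7.1), so a short early course for another illness need not affect a later score.
- That every affected subject inflates the rate. One who had already responded before the new therapy adds nothing.

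**Conclusion.** The point holds as a gap in the scoring of the responder endpoints. For subjects withdrawn because of new PN or itch therapy, responder status is unstated, and the choice of denominator is worth +1.0 to +6.5 points under the assumed counts, or nothing if all 25 are kept. For the smaller group who stay on study drug, the stated rule credits assisted itch to upadacitinib, at 4 points per subject converted; the 12-point extreme needs three affected subjects and full conversion.

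These sizes rest on assumed frequencies, and the true number could be zero. It would be wrong to infer that a conclusion of the study is at risk: it is exploratory and sets no threshold. What suffers is the reading of the reported rate, particularly if the scoring is settled after open-label results are known. This is a cheap improvement.

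**What to change.** Add to section 8.2.1:

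> For the WI-NRS, IGA PN-S and IGA PN-A responder endpoints the denominator is all enrolled subjects who received study drug. A subject who newly starts a therapy for PN or its itch (other than study drug and the moisturizer) before an assessment is a non-responder at that and later assessments, including if then withdrawn. A sensitivity analysis uses observed scores.

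List systemic corticosteroids and immunosuppressants given for another illness. Handle them in a sensitivity analysis that treats as non-response only scores taken during such use or within a stated washout, and do not make them permanent failures in the primary analysis.

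In section 5.6.8, state which therapies are unapproved. The scoring rule itself withdraws nobody.

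The cost is wording plus a medication flag. Section 8.3 already records concurrent medication at every visit, but the flag needs the indication and start date of each new drug, which the documents do not say are captured. The reported rate may be slightly lower: 1/25, or 4 points, for each subject who had already responded before starting such therapy. The observed-score analysis shows how much that matters. The rule does not reach a dose increase of a drug already in use at baseline.

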### **5.6 Study Procedures**

This protocol will consist of a Screening Period (0-30 days), followed by open label treatment period of upadacitinib 15mg-30mg QD for 24 weeks. To date, Dupixent is the first and only medication to demonstrate positive results in prurigo nodularis at week 24 and receive regulatory approval for PN. This study will explore efficacy over a 24-week period to evaluate clinical response.

This Study will be conducted in compliance with CFR Title 21, Part 50 (Informed Consent of Human Subjects). Informed consent will be obtained from each subject in writing before participation in the Study. A signed copy of the Informed Consent Form will be provided to each subject. A provision to obtain a signed authorization to provide protected health information to the study sponsor, internal quality assurance agencies, health

insurance agencies, and other parties as specified in the Federal Health Insurance Portability and Accountability Act (HIPAA) privacy regulation will be included in the Informed Consent Document. HIPAA authorization is voluntary. However, since the use and release of health information is critical to the conduct of the study, subjects who do not provide authorization to use and disclose their health information will not be enrolled into the study. Subjects who withdraw their authorization to use and release health information during study participation will be formally discontinued from the study. The investigator may use and release at any time all the information collected prior to a subject's withdrawal of the authorization to all authorized parties to satisfy scientific, regulatory, and financial concerns.

### **5.6.1 Inclusion and Exclusion Criteria**

Subjects' eligibility to participate in the study will be determined according to the Inclusion and Exclusion Criteria during the screening period (0 – 30 days prior to the first dose of the study drug). Subjects who ultimately do not satisfy the eligibility criteria except changing treatments and undergoing a washout period, will not be enrolled into the study. Subjects who need to meet eligibility requirements will be asked to make the necessary changes. Subjects who agree and comply will be re-evaluated prior to Baseline.

### **5.6.2 Demographics and Medical History**

The following information will be obtained for each subject during screening: date of birth, sex, race/ ethnic origin, relevant medical and surgical history, including year of diagnosis of prurigo nodularis, and current and previous prurigo nodularis treatments for the last 6 months. All current therapies for other medical conditions will be documented. Medical history will be reviewed and updated at the Baseline Visit to ensure that the patient remains eligible to participate in the study.

### **5.6.3 Pregnancy Testing**

Serum Pregnancy testing (urine  $\beta$ -human chorionic gonadotrophin [ $\beta$ -HCG]) will be conducted in all female subjects, except those without childbearing potential at Screening (-30 to -1). Urine pregnancy tests will be conducted at Baseline (prior to first dose of upadacitinib) and at each visit through week 24. An interim urine pregnancy test may be performed if there is reason to believe the subject may have become pregnant during the study. Subjects with a positive pregnancy test will not be eligible to participate or to continue to receive study treatment.

### Contraception Requirements for Females

A female who is permanently surgically sterile or postmenopausal is not considered to be a female of childbearing potential and is not required to follow contraception recommendations.

Surgically sterile is defined as:

- bilateral oophorectomy (surgical removal of both ovaries); or
- bilateral salpingectomy (surgical removal of both fallopian tubes); or
- hysterectomy ( surgical removal of uterus)

Postmenopausal is defined as:

- Age  $\geq$  55 years with no menses for 12 or more months without an alternative medical cause; or.
- Age  $<$  55 years with no menses for 12 or more months without an alternative medical cause AND a follicle-stimulating hormone (FSH) level  $>$  40 IU/L.

If the female subject is  $\leq$  55 years of age, postmenarchal, and has had no menses for  $\geq$  12 months AND has no history of permanent surgical sterilization (defined above), FSH should be tested at Screening.

- If FSH is not tested, it is assumed that the subject is of childbearing potential and protocol specified contraception is required.
- If the FSH is tested and the result is consistent with postmenopausal status, contraception is not required.
- If the FSH is tested and the result is consistent with premenopausal status, contraception is required, and pregnancy testing requirements for women of childbearing potential must be followed (see below).

A female who does not meet the definition of postmenopausal or permanently surgically sterile is considered of childbearing potential and is required to practice at least one of the following highly effective methods of birth control that is effective from Baseline Visit (or earlier) through at least 30 days after the last dose of study drug.

- Combined (estrogen and progestogen containing) hormonal contraception (oral, intravaginal, transdermal) associated with the inhibition of ovulation, initiated at least 30 days prior to Baseline Visit.
- Progestogen-only hormonal contraception (oral, injectable, implantable) associated with inhibition of ovulation, initiated at least 30 days prior to Baseline Visit.
- Bilateral tubal occlusion/ligation.
- Vasectomized partner(s) provided the vasectomized partner has received medical confirmation of the surgical success and is the sole sexual partner of the women of childbearing potential trial participant.

- Intrauterine device.
- Intrauterine hormone-releasing system.
- True abstinence (if acceptable per local requirements): Refraining from heterosexual intercourse when this is in line with the preferred and usual lifestyle of the subject. Periodic abstinence (e.g., using calendar, ovulation, symptothermal, postovulation methods) and withdrawal are not acceptable.

If required per local guidelines, male or female condom with or without spermicide OR cap, diaphragm or sponge with spermicide should be used in addition to one of the birth control methods listed above (excluding true abstinence).

If during the course of the study a female becomes surgically sterile or postmenopausal (defined above) and complete documentation is available, contraceptive measures as defined above are no longer required. It is important to note that contraception requirements described above are specifically intended to prevent pregnancy during exposure to the investigational therapy upadacitinib.

Contraception recommendations related to use of concomitant therapies prescribed per standard of care should be based on the local label.

Additional local requirements may apply.

At each visit, the study staff should review the pregnancy avoidance recommendations with each female of childbearing potential and document this discussion in the subject's source records.

#### **5.6.4 Laboratory Testing**

Serum chemistry, hematology, Hepatitis B Surface Antibody and Antigen (HBV), Hepatitis C Antibody (HCV) and Quantiferon Gold testing will be performed at screening to ensure subject safety prior to baseline. Serum chemistry and hematology will also be performed at weeks 12 and 24.

